## 9. STATISTICAL METHODS

### 9.1. General Considerations

Data will be summarised using descriptive statistics (n, mean, median, standard deviation, minimum, maximum) for continuous variables and frequencies and percentages for discrete variables. Time to event variables will be summarised using the Kaplan-Meier method. All data summaries and listings will be produced using the SAS® software Version 9.4 or higher. A separate statistical analysis plan (SAP) will be prepared describing more details.

### 9.3. Analysis Populations

Safety Population: Consists of all subjects who receive at least one dose of study drug.

PK Analysis Population: Subjects in the safety population who have at least one measurable post-EQ101 exposure concentration.

### 9.4. Statistical Analysis Methods

#### 9.4.1. Safety Analyses

AEs will be coded using the Medical Dictionary for Regulatory Activities (MedDRA) for the purposes of summarisation. TEAEs, AEs that start during or after the first dose of study drug or AEs with an onset prior to the first dose of study drug that worsen after study drug administration, will be summarised by system organ class (SOC) and preferred term (PT). Treatment-emergent serious AEs (TESAEs), TEAEs leading to treatment discontinuation, and TEAEs with an outcome of death will be summarised similarly. In addition, TEAEs will be further summarised by worst severity grade and relationship to study drug. AEs of special interest (AESI) will be summarised by SOC, PT, and worst severity grade.

Clinical laboratory data will be summarised descriptively including observed values at collection timepoints and change from Baseline. All laboratory parameters that can be graded using CTCAE v5.0 will be graded. Other safety measures including vital signs and physical examination findings will be listed and summarised as appropriate.

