### 2.2. Study Endpoints

#### 2.2.1. Primary Endpoints

The primary endpoints of the study are:

- incidence, severity, and relationship of TEAEs, SAEs, TEAEs leading to discontinuation of study treatment;
- changes in vital sign measurements;
- changes in ECG parameters; and
- changes in clinical laboratory results.

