COVID-19 infection, infection requiring treatment with systemic antibiotics, antivirals, antiparasitics, antiprotozoals, or antifungals within 14 days before the first dose of study drug or a major episode of infection that required hospitalisation or treatment with IV antibiotics within 60 days before the baseline visit. Or serologic evidence of HBsAg, HCV or HIV, including during screening.
25. Abnormalities in clinical laboratory tests at Screening, as confirmed by a single repeat, if deemed necessary:
  - a. Absolute neutrophil count (ANC)  $<1.0 \times 10^9/L$ .
  - b. Liver function tests (LFTs including ALT and AST)  $>3 \times$  upper limit of normal (ULN).
  - c. Total bilirubin  $>1.5$  times ULN (unless isolated Gilbert's syndrome)
  - d. Serum creatinine  $>1.5$  ULN.

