#### 6.3.1. Adverse Events

An AE is any untoward medical occurrence in a clinical study participant administered a pharmaceutical product and which does not necessarily have a causal relationship with this treatment.

An AE can therefore be any unfavourable and unintended sign (including an abnormal laboratory finding), symptom, or disease temporally associated with the use of a medicinal (investigational) product, whether or not related to the medicinal (investigational) product (definition per International Council for Harmonisation [ICH]). Pre-existing events, which increase in frequency or severity or change in nature during or because of use of a drug in human clinical studies, will also be considered as AEs. AEs may also include pre- or post-treatment complications that occur as a result of protocol-mandated procedures (e.g., invasive procedures such as biopsies).

AEs will be monitored throughout the entire study. Investigators will ask the subjects at each visit if they have experienced any untoward occurrence since the last study visit. All AEs will be recorded on the CRFs provided, including: a description of the event, severity, time of occurrence, duration, any action (e.g., treatment and follow-up tests), outcome, and the Investigator's assessment of the relationship to the study treatment.

From the time of signing the ICF through the first study drug administration, all SAEs and nonserious AEs related to protocol-mandated procedures (including medication washout performed specifically for the study) will be recorded on the SAE/AE eCRF. All other untoward medical occurrences observed during Screening, including exacerbation or changes in the medical and surgical history, will be captured on the medical and surgical history eCRF. An AE does not include:

- medical or surgical procedures (i.e., surgery, endoscopy, tooth extraction, transfusion); the condition that leads to the procedure is an AE;
- pre-existing diseases or conditions present or detected prior to start of study drug administration which do not worsen;
- situations where an untoward medical occurrence has not occurred (i.e., hospitalisation for elective surgery [prolongation of hospitalisation is an AE], social and /or convenience admissions); or
- overdose of either study drug or concomitant medication without any signs or symptoms, unless the subject is hospitalised for observation.

A clinical abnormality that meets any of the following criteria should be reported as an AE:

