- has accompanying symptoms and signs;
- requires additional diagnostic tests or therapeutic measures (e.g., surgical intervention);
- leads to a change in study drug dosing regimen (e.g., dose delay, discontinuation) or study termination; or
- is considered clinically significant by the Principal Investigator (PI).

Any AE where a causal relationship with the study drug is a reasonable possibility (possibly/probably or definitely related) is referred to as an **adverse drug reaction**.

An **SAE** is any AE that, at any dose:

- results in death;
- is life-threatening (the term 'life-threatening' in the definition of 'serious' refers to an event/reaction in which the participant was at risk of death at the time of the event/reaction; it does not refer to an event/reaction which hypothetically might have caused death, if it were more severe);
- requires inpatient hospitalisation or prolongation of an existing hospitalisation (only hospitalisations that are longer than expected based on PI judgement, will be considered prolonged hospitalisations);
- results in persistent or significant disability/incapacity (an AE that results in a substantial disruption of a person's ability to conduct normal life functions); or

- is a congenital anomaly/birth defect (a congenital anomaly/birth defect that occurs in the offspring of a participant exposed to the study drug).

Medical and scientific judgement should be exercised in deciding whether other situations should be considered serious, such as important medical events that may not be immediately life-threatening or result in death or hospitalisation but might jeopardise the participant or might require medical or surgical intervention to prevent one of the other outcomes listed in the above definition. These should also be considered serious.

Examples of such events are intensive treatment in an emergency room or at home for allergic bronchospasm, blood dyscrasias or convulsions that do not result in hospitalisation, or development of drug dependency or drug abuse.

A sudden unexpected serious adverse reaction (SUSAR) is an AE that meets all the following criteria:

- is serious;
- there is at least a reasonable possibility of a causal relationship between the event and the study drug;

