6.2 General Considerations

All data collected during the study (data originating from the electronic Case Report Forms (eCRFs) or electronic transfers will be presented in the data listings. Event-based listings will be sorted by subject identifier and event start date/time (i.e., Adverse Event (AE) start date/time). Assessment-based listings will be sorted by parameter name (alphabetically unless specifically stated otherwise), subject identifier, visit, assessment date and time (if applicable).

Unless otherwise stated, the following methods will be applied:

- Continuous variables: Descriptive statistics will include the number of non-missing values (n), arithmetic mean, standard deviation, median, minimum, and maximum values.

The minimum and maximum values will be displayed to the same decimal precision as the source data, the arithmetic mean and median values will be displayed to one more decimal than the source data, and the standard deviation (SD) values will be displayed to two more decimals than the source data for the specific variable.

The appropriate precision for derived variables will be determined based on the precision of the data on which the derivations are based, and statistics will be presented in accordance with the abovementioned rules.

- Categorical variables: Descriptive statistics will include frequencies and percentages per category. The denominator in all percentage calculations will be the number of subjects in the relevant analysis population, unless specifically stated otherwise. Percentages will be rounded to one decimal place and will not be displayed for zero frequencies.
- Repeat/unscheduled assessments: When values collected at scheduled study visits/time points is missing, repeat or unscheduled assessments closest to the scheduled visit date within the visit window defined in Table 1 and Table 2 will be used for the visit to calculate summary statistics in summary tables with visits as defined in section 6.6. All collected data will be included in the data listings. If an unscheduled visit was intended to replace the missing assessment for a scheduled visit this should be documented clearly before values are used as a scheduled visit assessment.

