17.2 Safety Laboratory Assessments

For the haematology, serum chemistry and coagulation, continuous data summary statistics (as described in Section 6.2) and count and percentages of normal and abnormal (defined by a test-specific normal range) will be presented for values, change from baseline at each visit.

In addition, Shift from Baseline at each visit for haematology, serum chemistry and coagulation lab parameters (low, normal, high) will also be presented using counts and percentages in shift tables.

For urinalysis and urine microscopy, continuous data summary statistics (as described in Section 6.2) and count and percentages of normal and abnormal will be presented for values at each visit.

The listings of laboratory parameters (haematology, serum chemistry, coagulation, and urinalysis) will include all the information collected. In addition, the observations that are used as the baseline record (value) for each parameter will be flagged, and the change from baseline values (where applicable) at each post baseline (scheduled and unscheduled) visit will be presented. These listings will be presented sorted by Subject ID and assessment date for the Safety Population, along with age, sex, race, and baseline weight of the subject.

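### SAP 17.1–17.2 do not carry over protocol 9.4.1's CTCAE laboratory grading or its SOC/PT table of TEAEs leading to discontinuation, and no laboratory table summarises each subject's worst change

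*Protocol*

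**What the plan says.** Protocol 9.4.1 (repeated in the synopsis) makes four commitments that matter here.

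- Laboratory: "All laboratory parameters that can be graded using CTCAE v5.0 will be graded".
- TEAEs leading to treatment discontinuation are summarised in the same way as TEAEs overall, that is by SOC and PT.
- AESIs are summarised by SOC, PT and worst grade.
- TEAEs are further summarised by worst grade.

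Protocol 2.2.1 makes TEAE severity, TEAEs leading to discontinuation and "changes in clinical laboratory results" primary endpoints.

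SAP 17.2 gives continuous summaries for haematology, chemistry and coagulation, and "count and percentages of normal and abnormal (defined by a test-specific normal range) will be presented for values, change from baseline at each visit". It adds a shift table: "Shift from Baseline at each visit for haematology, serum chemistry and coagulation lab parameters (low, normal, high) will also be presented using counts" and percentages. Its listings are sorted by subject and date, flag the baseline record, and show change from baseline at scheduled and unscheduled visits.

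For summary tables, SAP 6.2 brings in other draws only as substitutes: "When values collected at scheduled study visits/time points is missing, repeat or unscheduled assessments closest to the scheduled visit date within the visit window" are used.

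SAP 17.1 specifies six SOC/PT tables: TEAEs, TEAEs by grade, TEAEs by relationship, serious TEAEs, treatment-related TEAEs, and treatment-related TEAEs by grade. TEAEs leading to study drug withdrawal have a row in the overall summary and a separate listing.

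**The concern.** SAP 23 bases the final analysis on the final SAP, so a protocol analysis that the SAP leaves out is likely not to be produced. Here the omissions touch primary safety endpoints.

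The laboratory gap has a specific consequence in this trial. Exclusion 25 in protocol 4.1.2 removes subjects only above 3 x ULN for ALT/AST and above 1.5 x ULN for creatinine and for bilirubin (isolated Gilbert's syndrome excepted). Subjects can therefore start above the normal range. For them a low/normal/high shift table cannot show worsening, because high-to-high is not a shift. The maximum at each visit would show an extreme value at a scheduled draw, but not how many different subjects reached one over 24 weeks.

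**Working it through.** **Protocol against SAP**

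| Protocol 9.4.1 | SAP 17.1–17.2 |
|---|---|
| CTCAE v5.0 grading of gradable laboratory parameters | Not specified; classification is by normal range only |
| SOC/PT summary of TEAEs leading to discontinuation | Overall row and listing; no SOC/PT table |
| AESI summary by SOC, PT and worst grade | Not specified |
| TEAEs by worst grade | SOC/PT table by Grade 1 to 5; worst grade not stated |

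Neither CTCAE nor AESI occurs in the visible SAP text or its abbreviation list.

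On the last row, protocol 6.3.5 requires each increase in severity to be a separate AE record. A subject whose event goes from Grade 1 to Grade 2 therefore has the same PT at two grades. SAP 17.1 counts a subject once for a repeated event but does not say at which grade. SAP 12 does state a worst-status rule, for medical history.

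**What by-visit laboratory tables can miss**

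This illustration bears only on the value of a worst-post-baseline table. Its inputs are assumed, because the laboratory visit schedule and the CTCAE cut-offs are not in the visible text. Take 30 subjects and 4 scheduled laboratory visits. Baseline ALT is 2.5 x ULN in 4 subjects and 0.5 x ULN (taken as normal) in 26, who do not change.

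- Case A: one of the 4 is at 10 x ULN at all 4 visits; the other 3 stay at 2.5.
- Case B: each of the 4 is at 10 x ULN at a different visit and at 2.5 otherwise.

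At every visit both cases hold the same values: one 10, three 2.5, twenty-six 0.5.

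- Mean = (10 + 3 x 2.5 + 26 x 0.5)/30 = 30.5/30 = 1.02.
- Sum of squares = 100 + 18.75 + 6.5 = 125.25. SD = sqrt[(125.25 − 30.5²/30)/29] = 1.80.
- Median 0.5; maximum 10.
- Change is +7.5 once and 0 twenty-nine times. Mean = 7.5/30 = 0.25; SD = sqrt[(56.25 − 7.5²/30)/29] = 1.37; maximum +7.5.
- Four subjects are abnormal, all four high-to-high, and none shifts category.

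Subjects who ever reach 10 x ULN: A 1/30 = 3.3%, B 4/30 = 13.3%. Spreading the four peaks over 2 or 3 subjects gives the same by-visit tables with 2/30 = 6.7% or 3/30 = 10.0%. So the tables fit anything from 3.3% to 13.3%.

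CTCAE grades tabulated by visit would also be equal in A and B, since values and baselines match at every visit. A table of baseline by worst post-baseline value separates them.

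If instead the peaks fall at unscheduled draws and all scheduled values equal baseline, the summaries show mean (4 x 2.5 + 26 x 0.5)/30 = 23/30 = 0.77, maximum 2.5 and change 0 at every visit.

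**The case against.** The strongest reply is that little is lost. The listings give every subject's change from baseline at each scheduled and unscheduled visit, and with about 30 subjects they can be read in full. A large rise would probably also become an AE. Protocol 6.3.1 says "A clinical abnormality that meets any of the following criteria should be reported as an AE", and one criterion is that it "requires additional diagnostic tests or therapeutic measures". The discontinuation listing carries PT, SOC, severity and causality for what may be only a few events. The protocol already states the worst-grade rule, and the SAP does not contradict it.

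Much of this stands, and it rules out several stronger readings.

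- A reader might infer that the SAP gives no per-subject view of laboratory worsening. It does, in the listings; only a summary table is missing.
- A reader might infer that SAP 17.1 gives only overall AE counts. Its six SOC/PT tables cover grade, relationship and seriousness.
- A reader might take cases A and B as the effect of omitting grading. They are not. The protocol promises grading and no particular table by grade, and by-visit grading would leave the two cases alike.
- A reader might infer that fatal TEAEs are uncovered. There is no separate SOC/PT table, but the serious-TEAE table, the Grade 5 level, the overall death row and the death listing largely cover them.

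The AE backstop is only partial. Protocol 6.3.9 leaves reporting of laboratory values as AEs to the investigator's discretion and allows the clinical sequelae to be recorded in place of the abnormality. Listings also do not replace a summary that the protocol says will be made.

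The AESI item is weaker because no AESI list is visible. SAP 17.1 does list infusion-site, infusion-related and hypersensitivity reactions separately, and protocol 8.1 singles out infusion-related and hypersensitivity reactions for close monitoring. The documents do not say whether these are the AESIs.

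**Conclusion.** The point holds as a mismatch between protocol and SAP that should be fixed. Two items carry the weight: CTCAE v5.0 laboratory grading and the SOC/PT table of TEAEs leading to discontinuation, both stated in protocol 9.4.1 and absent from SAP 17.1–17.2. The AESI table and the worst-grade counting rule are lesser alignment items.

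The lack of a per-subject summary of worst laboratory change is a separate weakness of the by-visit design. It goes beyond what the protocol promises. Its size in this trial cannot be known from the documents; the 3.3% to 13.3% range rests on the assumed baselines, peaks and visits. No data are lost and no trial conduct is affected.

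Other parts of the public SAP are blacked out, so a declared change from the protocol there cannot be excluded.

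**What to change.** In SAP 17.2:

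- Grade all gradable laboratory parameters by CTCAE v5.0, as the protocol states.
- As an improvement on that commitment, tabulate baseline grade by worst post-baseline grade per subject, including unscheduled values.

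In SAP 17.1:

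- Add a SOC/PT table of TEAEs leading to study drug discontinuation.
- State that severity tables count each subject once, at worst grade, within each SOC and each PT.
- Add the AESI table by SOC, PT and worst grade with a reference to the AESI list, or document its omission as a change from the protocol.

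Any other item left out should likewise be recorded as a change from the protocol. The cost is SAP wording and a few extra tables from data already collected.

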#### 9.4.2. Efficacy Analyses

Efficacy measures will be collected for all subjects. Efficacy measures include the SALT score [REDACTED] ClinRO measures for EB, EL and body hair loss evaluated by the Investigator and PRO measures. The Scalp PRO tool and ClinRO/PRO measures for EB and EL hair loss are

validated outcome measures [REDACTED] Efficacy endpoints will be summarised in the safety population using methods described in the General Considerations section.

#### **9.4.3. Pharmacokinetic (PK) Analyses**

Plasma concentrations of EQ101 will be reported as listings for individual subjects and also as statistical summaries grouped by the scheduled timepoint. The statistical summary will include mean, standard deviation (SD), coefficient of variation (CV%), maximum, minimum, median, geometric mean, and geometric CV%.

Plasma concentrations of EQ101 from this study may be included in a population PK analysis in order to generate PK parameters that will be documented in a separate Population PK Report

[REDACTED]

[REDACTED]

[REDACTED]

[REDACTED]

## **10. ADMINISTRATIVE CONSIDERATIONS**

### **10.1. DATA HANDLING AND RECORDKEEPING**

#### **10.1.1. Privacy of Personal Data**

In order to maintain subject privacy, all eCRFs, study treatment accountability records, study reports and communications will identify subjects by only their assigned subject study number. The PI will grant monitor(s) and auditor(s) from the Sponsor (or designee) and regulatory authorities access to the subject's original medical records for verification of data gathered on the eCRF and for the purposes of auditing the data collection process. The subject's confidentiality will be maintained at all times and will not be made publicly available to the extent permitted by the applicable laws and regulations.

#### **10.1.2. Screening/Enrolment Logs and Privacy**

The PI is required to complete a subject enrolment log to permit reference to each subject during and after the study. Any log identifying study subject identity will be treated as confidential and will be filed by the PI in the Investigator Site File (ISF). This document will be reviewed by the Study Monitor for completeness. To ensure subject confidentiality, if such a log is required to be distributed to the Sponsor, it must first have any personal details (e.g., name, initials, date of birth) redacted.

The PI must also complete a volunteer screening log, which reports on all volunteers who were assessed to determine eligibility for inclusion in the study.

#### **10.1.3. Source Documentation**

Source documentation must be prepared and available to capture at a minimum the following aspects and parameters:

- adherence to protocol procedures;
- participant study reference number(s);
- informed consent procedures;
- eligibility assessments;
- protocol specified schedules and assessments;
- dates of visits;
- safety observations including reporting and follow up of AEs;
- drug receipt/dispensing/return records;
- study treatment administration information;
- date of participant completion;
- discontinuation from treatment, or withdrawal from the study, and the reason if appropriate;

Specific items required as source documents will be reviewed with the PI before the study.

The author of an entry in the source documents must be identifiable. Worksheets may be used for the capture of some data to facilitate completion of the eCRF. Any such worksheets will become part of the subjects' source documentation.

Following the ICH-GCP guidelines, direct access to source documentation and medical records must be allowed for the purpose of verifying that the data recorded in the eCRF are consistent with the original source data.

#### **10.1.4. Electronic Case Report Form**

An eCRF entry must be completed for each subject who signs consent and commences screening for the study. For reasons of confidentiality, the name and initials of the subject should not appear in the eCRF. All eCRF entries, corrections, and alterations must be made by the PI or other authorised study-site personnel.

Data entry into the eCRF will be conducted throughout study conduct according to the Sponsor's (or delegate) instructions and reviewed by the Sponsor (or delegate) to determine their acceptability. If necessary, eCRF queries will be raised by the Sponsor (or delegate) relating to eCRF data entries. The PI or authorised study site staff must address all eCRF queries raised.

